Depression and anxiety are additional significant and common comorbidities associated with IPF. (5,6) A prevalence study consisting of 112 Korean patients with IPF showed that 25% experienced symptoms of depression and 21% experienced symptoms of anxiety. Survival rates and rates of hospitalization did not significantly differ between patients with and without depression and/or anxiety, however patients with depression and/or anxiety reported poorer quality of life. (7)

Quality of life is significantly affected due to the grim outcomes associated with the diagnosis, disease symptoms (shortness of breath, hypoxia, and cough), managing multiple comorbidities, hospitalization rates and disease severity. (8) Hypoxia requiring long-term oxygen therapy (LTOT) has a particularly

large influence on quality of life, as patients must maneuver heavy equipment that typically includes tanks and machines in order to perform the most basic activities; restrictions on mobility and activities of daily living continue to rise as oxygen liter flow requirements persistently increase throughout disease progression.

Hospitalizations are common in patients diagnosed with IPF, with hospitalization frequently resulting in death. An observational study in France examined a hospital database to describe reasons, outcomes, and costs of hospitalizations of patients diagnosed with IPF. Of over 6,000 patients identified, 87% were admitted for one or several acute events (including respiratory infections, pneumothorax, pulmonary embolism, myocardial infarction and other cardiac events such as heart failure, rhythm disorders, or pulmonary hypertension) with 36.5% of these being an acute respiratory worsening. 12% died on first admission with mortality increasing to 36.8% by Year 3. (9) A retrospective analysis of IPF patients managed by the University of California at Los Angeles reported 25.3% of their patients were hospitalized over the course of their lung disease, with 77.3% of these being respiratory-related. Mean survival following hospitalization for a respiratory-related event was very low at 2.8 months. (10)

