Telemonitoring with hand-held home spirometry has been shown to be a reliable and valuable tool for monitoring health in respiratory illnesses. Russell demonstrated that daily measurement of FVC in IPF patients is more sensitive than hospital-based measures in predicting prognosis and at time points earlier than had been possible with traditional periodic monitoring (16). Respiratory patients benefit from home spirometry use by predicting re-exacerbation (17), allowing earlier tapering of steroids (18), and decreased healthcare costs in both compliant and non-compliant cystic fibrosis patients. (19) Asthma patients reported home use of spirometry was 'not complicated' and the vast majority remained interested in using a home system of monitoring their lung disease. (20)

Combined structured telephone calls with telemonitoring demonstrate further benefit across chronic care conditions including respiratory-related diseases. Celler demonstrated significant drops in healthcare expenditures, reduced admission rates to hospitals, and reductions in hospital stays among patients with COPD, CAD, HTN, DM, and asthma (21). Inglis completed a meta-analysis of 41 randomized clinical trials of heart failure patients and showed that structured telephone calls with non-invasive home monitoring reduced the risk of all-cause mortality and heart failure related hospitalizations as well as improved quality of life, overall disease knowledge, and self-care behavior (22).

We propose that structured telenursing with non-invasive remote monitoring of newly diagnosed IPF patients will, due to improved levels of patient education and understanding, decrease hospitalizations for respiratory illness, decrease visits to emergency centers or urgent care centers, increase compliance with therapies such as medication, oxygen, and rehab, and ultimately increase quality of life. This increased education and oversight of patients by nurses and nurse practitioners trained in the management of patients with Idiopathic Pulmonary Fibrosis will allow for earlier recognition of complications and exacerbations that we hypothesize will ultimately show an impact on mortality.

Hypothesis

Telenursing with or without remote monitoring will reduce the rate of hospitalization, and positively affect other variables, as compared to usual care (control group).

Endpoints

Primary Endpoint

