1. To determine if the total number of hospitalizations related to respiratory event is lower in the interactive arms (Arm 2 and Arm 3) than in the control group (Arm 1).

Secondary Endpoints

1. To recognize, evaluate, and treat respiratory events through telecommunications with or without remote monitoring before the requirement of hospitalization or result of death.
2. To improve compliance in multiple areas noteworthy to IPF patients as measured by various means during clinic appointments to help guide further understanding and education:
 - a. IPF medication compliance – by patient report/diary
 - b. Laboratory follow up – by patient report and collection of laboratory reports
 - c. Attendance in pulmonary rehab or other formal exercise program – by patient report and/or collection of rehabilitation records
 - d. Supplemental oxygen use – by patient report
 - e. Management of comorbidities
 - i. GERD – by patient report of medication use and lifestyle changes
 - ii. OSA – by collection of compliance reports of pap therapy, or notes of such contained in office notes
 - f. Vaccines – by patient report
3. To improve quality of life scores as demonstrated by QOL questionnaires
4. To compare hospitalization parameters of “time to first hospitalization”, length of stay, number of hospitalizations per individual, and outcomes (such as quality of life post-hospitalization), discharge status [alive, deceased], discharged to [home, hospice facility].
5. To improve patient knowledge of lung disease, treatments, and management as demonstrated by self-report
6. To compare measurements obtained by clinic spirometry and home spirometry and clinic pulse oximetry and home oximetry.

Exploratory Endpoints

Exploratory endpoints will be collected to determine if the activities related to telehealth and remote monitoring will positively affect physiology and mortality.

1. To evaluate the difference in forced vital capacity (FVC) from baseline/diagnosis among the groups and as stratified by class
2. To evaluate the difference in walk distance in six minutes from baseline/diagnosis among the groups and as stratified by class

3. To compare findings in annual echocardiography in regards to right ventricular size and function and pulmonary hypertension from baseline/diagnosis among the groups and as stratified by class
4. To evaluate mortality differences among the groups and as stratified by class

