5. To evaluate patient management at ILD Center compared to outlying community centers among the groups and as stratified by class.
6. To evaluate a standardized protocol that includes a structured educational curriculum followed by a regularly timed disease-focused phone calls with protocolized interventions when disease progression is recognized.

Study Design

This is a single-center prospective randomized study to compare outcomes on hospitalization, healthcare compliance, and quality of life of telenursing with or without remote monitoring as compared to usual care. All patients diagnosed with IPF at the Vanderbilt Medical Center outpatient Pulmonary Clinic, who meet inclusion and exclusion criteria, will be asked to participate. Patients who agree to participate and sign consent will be randomized into one of three treatment arms: usual care (the control group), usual care with telenursing, usual care with telenursing and remote monitoring. Patients will be asked to participate in the study for at least one year. We expect to enroll 150 patients, or 50 patients into each arm.

Usual care (Arm 1) – Patients will continue to receive education in the clinic and telephonically about their lung disease, medications, and oxygen use. At the point of diagnosis, patients will be given our current educational materials to take home and review, as well as our contact information. Patients will continue to attend face-to-face visits in the out-patient setting. The frequency of visits will be based on the discretion of the provider. During these visits, the patient will continue to receive individualized standard of care, which may include some or all of the following: a face-to-face visit with a healthcare provider, vital signs, with pulse oximetry at rest, weight measurement, pulmonary function testing, a six-minute walk, and laboratory testing. Other testing, such as echocardiography or chest radiography, may be required based on need. If patients do not return to Vanderbilt Medical Center beyond the point of diagnosis, they will still be allowed to participate. The usual care of local healthcare providers will be collected.

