Data collected will include the following: demographics (gender, race, ethnicity, age at diagnosis, date of birth, miles from our center, classification of rural, suburban, or urban, tobacco use and status), diagnosis (date of diagnosis, where made, physician overseeing, where IPF healthcare will occur), longitudinal physiological components of IPF collected in the clinic or hospital (measures of pulmonary function, 6-minute walk, echocardiography, heartrate at rest, oxygen saturation at rest on room air/liter flow of oxygen, and body weight, as well as provider's interpretation of IPF classification/stage), daily physiological components as captured at home (FVC in liters, FEV1/FVC ratio, heartrate at rest, oxygen saturation at rest on room air/liter flow of oxygen), staging at clinic visits, use of FDA approved medications for IPF, hospitalizations (dates of admission and discharge to determine length of stay and time to hospitalization, and the admitting diagnosis), cost of hospitalizations, outcomes of telenursing calls, quality of life and other questionnaire scores, compliance measures (related to medications, pulmonary rehabilitation, oxygen use, and comorbidities such as GERD and OSA), and health status (living, deceased, transplanted). PHI collected will include date of birth, medical record number, date of diagnosis, and dates of service. No other standard PHI will be included.

Statistics

Power calculations for telenursing project

Simulation

In order to understand the operating characteristics of the proposed telenursing project, we constructed a simulation study. Using the Brown-2015 paper as the basis of the simulation study, we generated a hypothetical study cohort of 300 subjects (100 in each arm). The one-year hospitalization event rate was

set to 25% in the usual care arm (A1). The event rate in arm 2 (A2) and arm 3 (A3) was set to a range of values, as noted in results table below (“A2 risk” and “A3 risk”).

[figure not shown]

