We generated 4000 replicates of the hypothetical study cohort for each combination of event rates, i.e., the rows of the results table. In each replicate, we calculated the (a) overall treatment effect, (b) the A2 vs A1 effect, and (c) the A3 vs A1 effect. The effect estimates were calculated by fitting a logistic regression model, and corresponding tests were calculated with the Wald method. Power was calculated as the proportion of the 4000 replicates in which the treatment effect was significant at $\alpha=0.05$ type I error rate.

Results

The results are provided in the table below. In the plot, RR refers to the relative risk of arm 3 to arm 1. In the table and in the plot, relative risk (RR) is simply the ratio of the risk in arm 2 (or 3) divided by the risk in arm 1.

Code

```
plotstyle(style = upright); par(mar = c(3,3,2,1))
plot.new()
plot.window(xlim = sim_settings$N %>% range, ylim = c(0,1))
g <- sim_settings %>%
  as.data.table %>%
  `[,`(,lines(copy(N), copy(power), type = "b"),p2)
axis(1, at = sim_settings$N %>% unique)
axis(2)
box()
title(xlab = "N (per arm)", ylab = "Power")
g <- sim_settings %>%
  filter(N == max(N)) %>%
  as.data.table %>%
  `[,`(, text(N, power, "RR = " %|% round(rr2,2), adj= c(1,-1)))
```

The table and plot report the same information.

Sample Size	A1 risk	A2 risk	A3 risk	RR 2:1	RR 3:1	Power 3:2:1	Power 2:1	Power 3:1
50	0.25	0.23	0.22	0.93	0.86	0.07	0.05	0.06
100	0.25	0.23	0.22	0.93	0.86	0.08	0.06	0.08
150	0.25	0.23	0.22	0.93	0.86	0.09	0.06	0.10
200	0.25	0.23	0.22	0.93	0.86	0.11	0.07	0.13
250	0.25	0.23	0.22	0.93	0.86	0.12	0.07	0.15
300	0.25	0.23	0.22	0.93	0.86	0.14	0.08	0.17
50	0.25	0.22	0.19	0.87	0.75	0.10	0.05	0.10
100	0.25	0.22	0.19	0.87	0.75	0.14	0.08	0.17
150	0.25	0.22	0.19	0.87	0.75	0.21	0.10	0.26
200	0.25	0.22	0.19	0.87	0.75	0.25	0.11	0.32
250	0.25	0.22	0.19	0.87	0.75	0.31	0.14	0.39
300	0.25	0.22	0.19	0.87	0.75	0.36	0.15	0.45

Sample Size	A1 risk	A2 risk	A3 risk	RR 2:1	RR 3:1	Power 3:2:1	Power 2:1	Power 3:1
50	0.25	0.20	0.16	0.82	0.66	0.16	0.08	0.17
100	0.25	0.20	0.16	0.82	0.66	0.24	0.12	0.31
150	0.25	0.20	0.16	0.82	0.66	0.36	0.15	0.44
200	0.25	0.20	0.16	0.82	0.66	0.46	0.19	0.55
250	0.25	0.20	0.16	0.82	0.66	0.56	0.24	0.66
300	0.25	0.20	0.16	0.82	0.66	0.64	0.27	0.73
50	0.25	0.19	0.15	0.77	0.58	0.21	0.09	0.23
100	0.25	0.19	0.15	0.77	0.58	0.38	0.16	0.46
150	0.25	0.19	0.15	0.77	0.58	0.53	0.23	0.64
200	0.25	0.19	0.15	0.77	0.58	0.66	0.29	0.74
250	0.25	0.19	0.15	0.77	0.58	0.75	0.33	0.83

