300	0.25	0.19	0.15	0.77	0.58	0.84	0.38	0.90

At least 80% power for the joint treatment effect and the A3 vs A1 effect was achieved when the event rate was .25, .19, and .15 for the three arms, respectively. The power for the comparison between A2 and A1 was 0.38, which was the highest of all the situations considered.

Proposed statistical analysis plan for the primary endpoint

The primary endpoint will be an ordinal variable that is a composite of hospitalizations and death within one year of diagnosis. The categories of the ordinal variable will be: 0 hospitalizations & no death, 1 hospitalization & no death, ..., K hospitalizations & no death, and then death as the final category. This will order the patients from best to worst outcomes in a way that incorporates the possibility of death.

The primary endpoint will be analyzed with a cumulative probability ordinal regression model which includes treatment assignment indicators and relevant covariates, such as age, gender, race, and other measures of baseline disease severity like **time-since-diagnosis**. Continuous variables, such as age, will be included in the model with restricted cubic splines in order to allow for the possibility of a non-linear association with the outcome. Model diagnostics, such as DFBETAs, will be generated to identify overly influential observations.

Once the regression model diagnostics indicate the model is reasonably fit, the treatment effect will be tested with Wald statistics at the $\alpha=0.05$ type I error level. The first effect to be tested is the joint treatment effect. If the joint effect is significant, then A3 vs A1 and A2 vs A1 will be tested. If the joint effect is not significant, no additional pairwise comparisons will be tested. The sequential test strategy ensures that the type I error rate is preserved.

As a sensitivity analysis, we will analyze hospitalization rates (not the composite hospitalization and death) with a model similar to the one described above.

Every effort will be made to collect covariate information; however, if missing data exists in the analysis dataset, we will adjust the analysis described above and implement multiple imputation with predictive mean matching. At least 30 imputations will be generated.

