Power for proposed analysis. The proposed analysis is expected to be more powerful than the analysis simulated above because it uses an ordinal instead of a binary outcome. As such, the power calculations above serve as a lower bound for the analysis of the primary endpoint.

APPENDICES

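### The binary power table is not a lower bound for the ordinal primary analysis: the simulation has no deaths, and deaths that treatment does not change lower power

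*Combined protocol and SAP*

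**What the plan says.** The Simulation and Results parts of the Statistics section describe a binary one-year hospitalization outcome, logistic regression and Wald tests. The control risk is 25%, and the table runs from 50 to 300 patients per arm. Its best case (risks 0.25, 0.19 and 0.15) has joint power of 0.84 at 300 per arm and 0.21 at 50. Study Design gives the planned size: "We expect to enroll 150 patients, or 50 patients into each arm".

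The primary endpoint is different. It orders patients by number of hospitalizations, "and then death as the final category", and is analysed with a covariate-adjusted cumulative probability model. The paragraph on power for the proposed analysis then states that "the power calculations above serve as a lower bound for the analysis of the primary endpoint".

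On mortality, the background expects earlier recognition of complications that "we hypothesize will ultimately show an impact on mortality". The endpoint list places death among the exploratory endpoints: "To evaluate mortality differences among the groups and as stratified by class". Neither place gives a death rate or an effect size.

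**The concern.** An ordinal analysis can be expected to be at least about as powerful as a binary one when it adds detail to the same events. Here it also adds a new event, death, and ranks it worst. Patients whose death is unrelated to treatment carry no treatment signal, yet they hold the most extreme ranks and dilute the effect. Whether power rises or falls depends on how many patients die within a year, whether deaths follow admission, and whether treatment lowers death. The plan fixes none of these.

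This sentence is the plan's only statement about the power of its actual primary analysis. It tells the reader that the table is a floor, when the table is one point in a range.

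**Working it through.** **Inputs.** From the documents: two-sided α = 0.05; control risk 0.25; relative risks 0.77 and 0.58, giving risks of about 0.192 and 0.145; 1:1:1 allocation; 300 per arm (the table's largest size) and 50 per arm (planned). Assumed, because the documents give no values: one-year control-arm death rates d of 5, 10, 15 and 20%; admission counts 0, 1, 2, 3+ from a Poisson distribution matched to each arm's risk of at least one admission.

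**Reproducing the table.** A simulated three-arm logistic model at 300 per arm gives 0.836 (joint), 0.395 (A2 vs A1) and 0.902 (A3 vs A1), against the stated 0.84, 0.38 and 0.90. The stated joint column matches a likelihood-ratio test in all 24 cells. At 50 per arm the likelihood-ratio test gives 0.21, as tabulated, but the Wald test named in the text gives 0.17. The like-for-like Wald references are therefore 0.83 and 0.17.

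**Ordinal detail without deaths.** Joint power is 0.85–0.87 at 300 per arm and 0.18–0.19 at 50 (Poisson, with negative binomial counts as a check). The ordinal scale itself adds about 2 to 4 points at 300 and 1 to 2 at 50.

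**Why equal deaths dilute the effect.** Take d = 10%, independent of admission, A3 against A1.
- No deaths, odds ratio for any admission: (0.145/0.855) / (0.25/0.75) = 0.51.
- With deaths, risk of any event: A1 is 1 − 0.75 × 0.90 = 0.325; A3 is 1 − 0.855 × 0.90 = 0.2305.
- Odds ratio for any event: (0.2305/0.7695) / (0.325/0.675) = 0.62.
- Odds ratio at the death cut-point: 1.

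The proportional-odds model pools these cut-points. Its fitted odds ratio moves from 0.51 without deaths to 0.59 at 5% deaths and 0.66 at 10%.

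**Death scenarios.** Joint 2-df Wald test, unadjusted proportional-odds model, 20,000 replicates, d = 5/10/15/20%:

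| Scenario | 300 per arm | 50 per arm |
|---|---|---|
| (a) Equal deaths, independent of admission | 0.70/0.54/0.41/0.31 | 0.14/0.11/0.10/0.08 |
| (b) Half of control deaths follow admission, no direct effect on death | 0.75/0.65/0.56/0.48 | 0.15/0.14/0.12/0.10 |
| (c) 80% of control deaths follow admission, no direct effect | 0.80/0.76/0.73/0.70 | 0.16/0.16/0.15/0.14 |
| (d) Equal deaths, all in admitted patients (5 and 10% only) | 0.79/0.74 | 0.16/0.15 |
| (e) All deaths follow admission at constant fatality | 0.83–0.84 | 0.17–0.18 |
| (f) Independent deaths that fall by the same relative risks | 0.89/0.92/0.95/0.97 | 0.20/0.23/0.25/0.29 |

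In (b) and (c), with s the share of control deaths that follow admission, the death risk is s·d/0.25 after admission and (1 − s)·d/0.75 otherwise, the same in every arm. Scenario (d) stops at 10% because only 14.5% of A3 patients are admitted.

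A second set of runs for (a), with 70/20/10% of admitted patients having 1, 2 or 3+ admissions, gave 0.68/0.53/0.40/0.31 at 300 per arm. At only 2% deaths it gave 0.77, already below the binary 0.83.

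**Covariate adjustment.** One severity covariate was added (assumed log effect 0.5 or 1.0 per SD on admission and death; 2,000 replicates). With equal deaths of 5/10/20%, adjusted power is 0.71–0.78/0.53–0.56/0.27–0.31 at 300 per arm, against 0.88–0.94 without deaths. At 50 per arm it is 0.16/0.11–0.12/0.08, against 0.20–0.24.

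**Control rate (separate point).** The Simulation section takes the cohort cited as reference 10 as its basis and uses 25% at one year. The only hospitalization rate the protocol quotes from that cohort is "25.3% of their patients were hospitalized over the course of their lung disease, with 77.3% of these being respiratory-related", which gives 0.253 × 0.773 = 0.196 for respiratory admissions over the disease course. With the same relative risks, control rates of 19.6/15/10% give binary joint power of 0.70/0.55/0.37 at 300 per arm, against 0.83 at 25%.

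**The case against.** The strongest reply is that the damaging scenarios are the least plausible.

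- **Deaths and admission are linked.** The background reports 12% dying on first admission in one hospital database and a mean survival of 2.8 months after respiratory hospitalization in the other cohort. That favours (c) and (e) over (a). Scenario (d) requires fatality among admitted patients to rise from 20% in A1 to 34% in A3 at 5% deaths (0.05/0.25 and 0.05/0.145).
- **Only (a) and (d) hold deaths equal.** In A3, deaths fall to 0.86 of control in (b) and 0.69 in (c).
- **Adjustment helps.** With the same assumed covariate effects at 300 per arm (1,500 replicates), adjusted power is 0.82–0.86 in (c) at 5% deaths, 0.78–0.82 in (c) at 10%, and 0.85–0.91 in (e) at 5–10%.
- **High death rates are unsupported.** Eligibility excludes FVC below 40%, high resting oxygen need, acute exacerbation and recent respiratory hospitalization. No source in the documents supports 15–20%.
- **The consequence is limited.** No reading makes 50 per arm adequately powered.

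Much of this stands as a limit on size. Losses at 50 per arm should be read against 0.17, not 0.21, and in (c) they are only 1 to 3 points. None of it restores a bound: adjusted power in (c) at 10% deaths is still below the table's 0.84, and the plan states no death assumption that would exclude (a) or (b). A weak design does not justify calling its power figure a floor.

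The control-rate point is also fairly limited. The cited paper may contain a one-year figure that the protocol does not quote, and the 19.6% counts respiratory admissions only. It supports a request for the source, not a finding of error.

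**Conclusion.** The concern holds. The lower-bound statement does not follow from its stated reason and fails under ordinary assumptions about death. Across the unadjusted scenarios, joint power for the largest tabulated effect runs from 0.31 to 0.97 at 300 per arm (binary Wald reference 0.83) and from 0.08 to 0.29 at 50 per arm (reference 0.17). Power falls when treatment leaves deaths unchanged or lowers them clearly less than admissions. It is kept when death falls in step with admission, and rises when independent deaths fall by the same relative risks.

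Confidence is high that the bound is not guaranteed. The magnitudes rest on assumed death rates, count distributions and covariate effects, and the 50-per-arm figures are the more approximate because outcome categories can be empty at that size. The conclusion does not depend on the control-rate point.

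**What to change.** Delete the lower-bound sentence. Re-run the existing simulation with the planned ordinal model and Wald test at 50 per arm, covering:

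- a stated range of one-year death rates, for example 5–20%;
- deaths independent of admission and deaths following it;
- with and without a treatment effect on death.

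Give the source of the one-year 25% control rate and show power over a range that includes lower values, for example 10–25%. Report the resulting power range in place of the claim.

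The cost is a re-run of existing code and two or three sentences. Trial conduct does not change. The stated power becomes a range whose low end is less favourable than the table.
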